More specifically, the studies conducted over the past decade suggest that low-intensity (e.g., <2mA) transcranial electrical stimulation (tES) can influence behavioral performance on a wide range of tasks. However, there remains uncertainty regarding (1) the significant inter-individual variability in response to brain stimulation, (2) variability in neurophysiological effects regarding brain activity and inter-regional connectivity, (3) the magnitude, nature and duration of immediate- vs. after-effects of stimulation, (4) the role of task-type in response to stimulation, and even (5) the underlying mechanism(s) of the tES effects¹. Regarding tasks, one domain that has seen particularly limited investigation is the performance of complex tasks that require multiple cognitive capabilities to be used simultaneously. There are numerous examples, but tasks like robotic/teleoperation, navigation, etc. are all relevant. It is unknown what effect tES may have on such tasks, which can be highly relevant for operational settings. **This IRB protocol is designed to support multiple substudies to address the above research questions.**

II. SPECIFIC AIMS

- 1) Characterize the relationship between the type, location and intensity of stimulation on *behavioral responses*.
- 2) Characterize the relationship between the type, location and intensity of stimulation on regional *neurophysiological responses*.
- 3) Characterize the relationship between the type, location and intensity of stimulation on the *after-effects on performance*.

III. SUBJECT SELECTION

Initial substudies will be conducted on healthy volunteers. Later substudies will be conducted on select patient populations (added via protocol amendment).

Healthy volunteers

We will recruit healthy individuals, age 18-64. In some substudies, we will restrict this further to the age range of 25-55 as representative of the astronaut population, given our group's focus on spaceflight-relevant research.

Inclusion criteria:

- Aged 18-64 years.
- No history of head injury or other neurological or psychiatric disorders, particularly bipolar disorder ².
- No history of cardiac disease, including ischemic heart disease, arrhythmia, hypertension, or syncope.
- No metal implants in the head
- No implanted electronic devices.
- Not taking any drugs known to effect neural or cardiovascular function.
- Ability to give a written and dated informed consent.

Exclusion criteria:

- Smoking within the last year

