This follow-up will involve more detailed questions to determine suitability for study enrollment, clarifying responses provided during initial screening, and answering any remaining questions they may have about the study. If the individual passes all eligibility criteria and is interested in participating, they will be provided with a copy of the consent form in advance and scheduled for study participation. Upon arrival, volunteers will be brought to the research exam room, where one of the investigators will explain the study in detail. In addition, the volunteer will be introduced to the behavioral tasks, the brain stimulation equipment, and the monitoring equipment to be used. Volunteers will be asked if they have questions about the study and express any concerns. They will also be informed of their right to withdraw from the study at any time. If they choose to participate, we will obtain their written informed consent, which will be countersigned by one of the study investigators.

c. Treatment assignment, and randomization (if applicable):

The study does not involve treatment assignment and/or medications, and each subject undergoing tES will have both active and sham conditions (i.e., they will serve as their own control). Therefore, treatment assignment and randomization is not applicable.

V. STUDY PROCEDURES

All investigations will involve computerized versions of standardized cognitive tests (e.g., N-back, continuous performance task, reaction time tasks, decision making tasks, spatial cognition, etc.) and/or more complex/operational performance tasks (e.g., robotic teleoperation, driving/navigation, or other computerized task).

Every study will involve two phases: (1) familiarization/training, (2) testing with/without brain stimulation. To address our aims regarding after-effects, some substudies will involve a third phase (3) post-testing without any additional brain stimulation. These phases will be described separately.

Phase 1 – Familiarization/Training: Tasks will be computerized tests that range from approximately 2-60 min in length. These will assess memory, attention, risk tolerance, executive function, and various other cognitive processes, sometimes in combination. For familiarization, subjects will have the computerized tasks explained to them, and then they will practice the tasks. Such familiarization/training sessions will take roughly 5-120 minutes, depending on the

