- *Stimulation session repetitions*: range=1-5 (again, remaining within the 60 min/day total stimulation limit); hence a maximum of 5 days of stimulation
- *Stimulation locations*: range=1-3; each subject will undergo tES over 1-3 different brain regions, but no more than 2 brain regions will be stimulated at the same time, always limited as described above.

Each subject will perform the task(s) from their familiarization/training session with stimulation, as well as without stimulation (sham) as part of Phase 2. We will counterbalance orders within/between subjects. A second stimulation period may be repeated on a given stimulation day, within the limits described above. The sham stimulation condition will follow the same procedure as the active condition, but stimulation will last only 30 seconds, ramping up and down at the beginning and end of the period to simulate the tingling sensation that subjects typically experience and then quickly habituate to during active stimulation ⁷.

Following each session, a safety questionnaire ⁸ will be administered, including questions regarding attention, concentration, mood, vision, headache, fatigue, and skin sensations under the stimulating electrodes.

Phase 3 - Post-testing: For studies investigating after-effects of stimulation, participants will perform the task(s) with physiological monitoring again without stimulation at up to 6 time points during the following week. Any interval >10 hours will be conducted during a separate visit the following day.

Overall Limits: Again, regardless of stimulation condition (stimulation or task duration, repetitions, or number of brain locations stimulated), no subject will exceed 2.0 mA peak-to-peak, 45 min in a single stimulation session or 60 min/day.

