Substudy 1: For this study, our primary outcome will be a 30 min computerized track-and-capture task battery involving dual-hand controllers. Phase 1 will last ~3 hours for consent, familiarization and task training. In Phase 2, subjects will undergo 45 min stimulation (or sham), perform the task battery, another 45 min of sham (or stim) one week later, and again perform the task battery. Stimulation will involve tDCS over the target location with a net intensity of 1.5-1.9mA depending on target and electrode configuration. Sham will involve the same electrode placements and the same 20-sec current ramp-up followed immediately by the 20-sec ramp-down. This generates sensory experiences similar to actual stimulation but without brain stimulation effects. Throughout Phase 2 we will record near-infrared spectroscopy (NIRS) over the prefrontal cortex, as well as 2-channel EEG (F3/F4), 1-channel ECG, 1-channel EMG, respiration, blood pressure, accelerometry and skin temperature. For Phase 3, subjects will be asked to return on two consecutive days after each stimulation to repeat the task battery and physiological monitoring (no brain stimulation on follow up days). This will result in a total of 7 visits over 11 days (Phase 1=~3 hours on day 1, Phase 2=~3 hours on day 2 and day 9, Phase

3~1 hour on each of days 3, 4, 10 and 11). For this substudy, N=20 subjects will be stimulated over the left dorsolateral prefrontal cortex (DLPFC), and a separate N=20 subjects will undergo stimulation over the left insular cortex. Electrode configurations for each location will be based on current source modeling with Soterix Medical's HD-Targets modeling software.

VI. BIOSTATISTICAL ANALYSIS

The specific metrics and our methods to calculate them appear below. All metrics will be cross-checked and verified prior to analysis. NINscan-derived measures will be processed programmatically to identify signal quality or dropout issues, any of which will be manually cross-checked, all per our prior work.

Preprocessing:

Performance Data: Behavioral task data will be evaluated per standard methods, typically summarizing accuracy and response time (e.g., ¹⁰) or summarizing various other continuous performance metrics such as smoothness of performance (e.g. ¹¹). This will provide a range of measures of individual cognitive capacities as well as operationally relevant performance metrics for both sham and stimulation conditions.

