NIRS: We will use the modified Beer-Lambert law to compute concentrations of oxy-, deoxy- and total-hemoglobin ([O₂Hb], [HHb], and [HbT] respectively). Close-detectors measuring scalp-only signals will be used as regressors to filter out systemic effects in most cases. The resulting data will be used to compute task-related functional activation, resting cardiac and vasomotor pulsatility, and inter-hemispheric functional connectivity at resting baseline, all per prior work ¹²⁻¹⁵.

Systemic Physiology: For ECG, we will compute average heart rate and heart rate variability via peak-detection algorithms. Respiratory rate and volume can be computed from the respiratory sensor. The accelerometer will be fed through a standard actigraphy algorithm ¹⁶. EEG will be examined through power spectral analysis after band-filtering to the frequencies of interest (e.g., 0.1-40 Hz).

Analysis:

We will first use descriptive statistics (means, standard deviations, skew, kurtosis) to characterize each metric within each subject and condition. Given the known speed-accuracy trade-off, we will make response time and accuracy the primary measures for each task (other metrics being secondary). We will then quantify the relationships between behavioral responses (Aim 1), neurophysiological responses (Aim 2) and after-effects on behavioral performance (Aim 3) as a function of type, location, intensity, and duration of brain stimulation. This will be conducted via mixed effects linear modelling approaches, with appropriate follow-up testing, including linearity, calibration, additivity, outliers, and post-hoc analyses to help identify nonlinearities such as onset of effects as a function of stimulation duration or intensity, and so forth.

We will report all p-values as uncorrected but include the number of statistical tests performed.

VII. RISKS AND DISCOMFORTS

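### Substudy 1 compares two stimulation sites between separate groups of 20, but the stated reason for not randomising covers only active versus sham, and no rule allocates participants to site

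*Combined protocol and SAP*

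**What the plan says.** Section IV.c declares that "treatment assignment and randomization is not applicable". The reason given is that each participant has both active and sham stimulation and so acts as their own control. The only balancing device in the protocol is under the tES protocol heading of Section V: "We will counterbalance orders within/between subjects". It concerns the order of conditions, not the site.

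Substudy 1 (Section V) stimulates 20 participants over the left DLPFC, and "a separate N=20 subjects will undergo stimulation over the left insular cortex". All active stimulation is tDCS for 45 minutes, at a "net intensity of 1.5-1.9mA depending on target and electrode configuration". Electrode configurations are described per location.

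Each of the three aims in Section II opens with "Characterize the relationship between the type, location and intensity of stimulation on", followed in turn by behaviour, neurophysiology and after-effects. Section VI plans mixed-effects linear models of these outcomes "as a function of type, location, intensity, and duration of brain stimulation". No separate model is given for Substudy 1, the only substudy described.

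**The concern.** Self-control justifies omitting randomisation only for a factor that varies within the participant. In Substudy 1 that factor is condition (active or sham). Site varies between participants, so the reasoning in Section IV.c does not reach it, and nothing else in the protocol does.

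Subtracting sham from active removes baseline performance differences between the two groups. It does not remove differences in how strongly the groups respond to stimulation. Section I lists variability between individuals in response first among its uncertainties. Eligible ages run from 18 to 64, and the series was projected to recruit from October 2020 to December 2025, so groups formed without a rule may differ in age, calendar time or responsiveness. Two such groups may show different stimulation effects even if site does not matter. At stake is the location part of the aims.

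A second gap follows from the missing Substudy 1 model. Two of the four predictors listed in Section VI have a single active level in this substudy, and a third may be tied to site.

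**Working it through.** The documents state no power, alpha, effect size or SD, so there is no figure of the plan's own to reproduce.

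**1. Which contrasts are exposed.**

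| Contrast | Varies | Covered by self-control? |
|---|---|---|
| Active vs sham, within DLPFC group | within participant, order counterbalanced | yes |
| Active vs sham, within insula group | within participant, order counterbalanced | yes |
| Condition x location | between participants, no allocation rule | no |

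**2. Precision of the site contrast.** Let s be the SD of the active-minus-sham difference. With 20 per site, the standard error of the difference between the two mean effects is s x sqrt(1/20 + 1/20) = 0.316 s, or about 0.32 SD.

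**3. Illustrative bias.** If the stimulation effect changes by b (in units of s) per SD of some participant characteristic, and the groups differ by m SD on it, the site contrast is biased by b x m. Both inputs are assumptions.

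| b | m | Bias (units of s) | Bias / 0.316 |
|---|---|---|---|
| 0.2 | 0.25 | 0.05 | 0.16 |
| 0.3 | 0.5 | 0.15 | 0.47 |
| 0.4 | 0.8 | 0.32 | 1.01 |

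Under randomisation m has mean zero and SD sqrt(2/20) = 0.316, so imbalance is chance variation that the standard error already reflects. Without an allocation rule, m need not centre on zero, and recruiting more participants would not remove the bias.

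**4. What Substudy 1 can estimate.** The fixed-effect matrix was built for 40 participants x 2 stimulation periods with counterbalanced order. Its columns were intercept, period, active, location and active x location, giving rank 5. Type, duration and intensity (all zero under sham) were then added.

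- Type has one active level (tDCS), so its column equals the active column. Rank stays 5.
- Duration has one active level (45 minutes), so its column is 45 x active. Rank stays 5.
- With one intensity per target, for example the two ends of the stated range, the intensity column is 1.5 x active + 0.4 x (active x location). Rank stays 5, and the full model has rank 5 from 8 columns. The same holds if everyone has one common intensity.
- If intensity varies between participants within a target, rank rises to 6 of 8 and intensity becomes estimable. The span is only 1.9 - 1.5 = 0.4 mA and is not randomised. With intensities simulated uniformly over the full range in both groups, the median standard error for the effect across 0.4 mA is about 0.57 s. With 1.5-1.7 mA at one site and 1.7-1.9 mA at the other, it is about 1.15 s, and the variance of the location contrast rises about 4.3-fold.

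A sequence column would not change the aliasing, because type and duration would still be exact multiples of active.

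**The case against.** The strongest reply is that this is a preliminary, hypothesis-generating programme. Substudy 1 states no between-site hypothesis and can be read as two parallel sham-controlled experiments, each internally valid. The point about the within-site contrasts stands in full: the missing allocation rule does not bias them. The parallel-experiments reading does not dispose of the concern, because all three aims name location and Section VI models it. Preliminary status may excuse low power, but it does not supply an allocation rule.

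Four stronger readings are tempting, and the documents do not support them.

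- A reader might infer that the plan promises type, intensity and duration effects from Substudy 1. Section VI is written for the whole umbrella series, and Section V allows three stimulation types and a range of durations across it. The gap is only that no Substudy 1 model is written.
- A reader might infer that intensity is necessarily inseparable from site. The text makes intensity depend on target and configuration, which suggests one value per target but does not say so.
- A reader might infer that the groups will differ, or that they are being filled in turn or by staff choice. The protocol simply does not say how they are filled. Bias arises only if something that modifies the response is imbalanced.
- A reader might infer that pooling with later substudies is bound to confound these terms with task and cohort. Those substudies are not described, and Section V allows one to three regions per participant, so location could vary within participant there.

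Two practical objections also stand. Randomising to site would not separate site from intensity if each target keeps its own intensity. And the protocol is dated April 2024 in a series projected to start in October 2020, so enrolment may already be too far on for a new list.

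**Conclusion.** The concern holds for the between-site contrast. The rationale in Section IV.c does not cover site, no rule replaces it, and location is a named aim with a place in the planned model. The size of the bias cannot be derived from the documents. The illustrative 0.15 SD (range 0.05 to 0.32 SD) rests entirely on assumed inputs and compares with a standard error of 0.32 SD. Even with sound allocation, the contrast would compare two montages, each possibly at its own intensity, rather than location alone.

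That type and duration cannot be estimated in Substudy 1 follows directly from its single type and single duration. The statement about intensity is conditional: fully aliased with condition and location if each target has one intensity, and otherwise weakly and only observationally estimable. The point bears on the location aim and does not call the sham-controlled results at either site into question.

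**What to change.** Amend Section IV.c so that Substudy 1 participants are randomised to target and sequence in one list, with both targets recruited concurrently: DLPFC or insula by active-first or sham-first, 40/4 = 10 per cell. If enrolment already makes this impossible, declare the two sites separate sham-controlled experiments, analyse each on its own, and draw no between-site inference, including none from comparing the two p-values.

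Add a Substudy 1 model to Section VI with condition, location, condition x location, period and sequence. Omit type and duration, and make no intensity-response claim from this substudy; the intensities used can be reported descriptively. State that the location contrast compares two montages, each as delivered.

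The cost is one allocation list and a paragraph of analysis text, with no extra participants or visits. The drawbacks are that both montages must be ready at the start and that the intensity claim is narrowed.
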